	
satisfactory pegasitacianine sensitivity and specificity values of 70% or greater in Part 1.
 
Patients will have a biopsy confirmed diagnosis, or a high clinical suspicion of a lung malignancy based on MRI, CT and/or PET imaging. A total of up to 40 patients will be enrolled in this trial across both parts. The sponsor reserves the right to perform an interim analysis following early enrollment (n ≤ 10 patients) to determine the feasibility and benefit of pegasitacianine as an adjunct to SOC surgery.
 
Parts 1 and 2:
 
The surgeon will attempt to perform their SOC resection of visible tumors. If the tumor is unable to be located using standard surgical approaches, an appropriate near-infrared (NIR) imaging device may be used to aid in localizing the primary tumor. Localization of the primary tumor using NIR imaging in conjunction with pathology confirmed presence of disease will be considered a clinically significant event.
 
If the primary tumor is located using standard operative procedures, the tumor will be imaged using the NIR camera and removed as per standard of care (i.e., wedge, lobectomy, etc.). The primary resection will then be imaged (front, back and margins) on a piece of normal tissue within the surgical field at a distance from the specimen equal to the working distance of the camera system. Inspection and imaging of the resection margins will be performed using the NIR camera system. If an area of suspicion is observed, images will be captured of the area, at the working distance of the camera away from the margin and documented for future correlation to pathological findings. Similarly, the in situ resection margin on the lung will be imaged for signs of residual fluorescence that may correspond to disease left behind. If found, images will be captured prior to the excision of the margin (in situ) and following its resection on a piece of normal tissue (ex situ). Resection of the suspicious or fluorescent margin is at the discretion of the surgeon. This procedure is to be repeated if additional SOC nodules are planned for resection. An identical approach will be followed for any SOC lymph nodes collected during the procedure. Lymph node imaging will occur prior to and following the removal of the suspected lymph nodes.
 
Once SOC surgical resection is complete, the surgeon will use the NIR camera system to evaluate the thoracic cavity (i.e., chest wall, contralateral lung, bronchi, etc.) for indications of residual fluorescence. If additional fluorescent foci are observed, the area may be resected, at the discretion of the surgeon, for pathological confirmation of disease. Similar to the imaging of margin resections, the suspected area will be imaged prior to removal (in situ) and following resection (ex situ) on a piece of normal tissue within the thoracic cavity. Additional fluorescent lymph nodes, detected during the evaluation of the thoracic cavity, may also be collected and imaged both in situ and ex situ prior to being evaluated in pathology.
 
Collected surgical specimens will be documented by the clinical research coordinator, as dictated by the surgeon in the provided Imaging Workbook. The fluorescence status of each specimen will be assessed and called out by the surgeon (fluorescent or not fluorescent), and similarly documented in the workbook. All samples will be sent to pathology for routine analysis. To determine the performance

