	
Once the patient is under anesthesia, some procedures will occur that would not normally be part of surgery if the patient were not in this study. The SOC surgical procedures will be allowed to continue with the addition of the steps listed below.
 

• If the primary tumor is not visually apparent using standard approaches, the NIR camera may be used to help locate and guide the resection of the primary tumor

• If the primary tumor is apparent under standard conditions, the suspected area will be imaged using the intraoperative camera prior to excision, and on a section of normal tissue at a distance equal to the working distance of the camera following excision

• Following the primary tumor resection, margins (both on the excised primary and the remaining lung) will be examined using NIR in an effort to detect the presence of a possible positive margin

• Any SOC lymph nodes that are to be collected will be imaged prior to, and following excision in a manner identical to that performed on the primary tumor specimen

• Once the SOC primary tumor and lymph node resection is complete, the surgeon will examine the thoracic cavity with the intraoperative NIR camera in search of additional fluorescent disease that was missed during SOC, or additional fluorescent lymph nodes

• Additional fluorescent lesions will be imaged prior to excision, removed, and then imaged on a section of normal tissue in a manner analogous to the SOC specimens.

 
Day of Discharge
 

• Record the patient's vital signs

• Perform a physical examination

• Discuss new or unexpected changes in they are feeling

• Obtain blood samples for routine laboratory tests

• Record all medications being taken, including prescription, over-the-counter, and herbal medications

• Discuss any new or unexpected changes

• Record any AEs

 
Day 21 (<math>\pm 10</math> days) after dosing
 

• Record the patient's vital signs

• Perform 12-lead ECG to monitor heart activity

• Perform a physical examination

• Discuss new or unexpected changes in how they are feeling

• Obtain blood samples for routine laboratory tests, including a pregnancy test for females who can become pregnant

• Record all medications being taken, including prescription, over-the-counter, and herbal medications

• Discuss any new or unexpected changes

• Record any AEs

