If the primary tumor is located using standard white light procedures, the tumor will be imaged using the NIR camera and removed as per standard of care (i.e., wedge, lobectomy, etc.). The primary resection will then be imaged (front and back) on a piece of normal tissue within the surgical field at a distance from the specimen equal to the working distance of the camera system. Inspection and imaging of the resection margins will be performed using the NIR camera system. If an area of suspicion is observed, images will be captured of the area at the working distance of the camera away from the margin and documented for future correlation to pathological outcomes. Similarly, the resection margin on the lung will be imaged for signs or residual fluorescence that corresponds to residual disease left behind. If found, images will be captured prior to the excision of the margin (*in situ*) and following its resection on a piece of normal tissue (*ex situ*). This procedure is also to be repeated if additional SOC nodules are planned for resection. An identical approach will be followed for the collection of any SOC lymph nodes collected during the procedure. Lymph node imaging will occur prior to and following the removal of the suspected lymph nodes.

Once SOC surgical resection is complete, the surgeon will use the NIR camera system to evaluate the thoracic cavity (i.e., chest wall, contralateral lung, bronchi, etc.) for indications of residual fluorescence. If additional fluorescent foci are observed, the area may be resected at the discretion of the surgeon for pathological confirmation of disease. Similar to the imaging of margin resections, the suspected area will be imaged prior to removal (*in situ*) and following resection (*ex situ*) on a piece of normal tissue within the thoracic cavity. Additional fluorescent lymph nodes, detected during the evaluation of the thoracic cavity, may also be collected and imaged both *in situ* and *ex situ* prior to being passed on to pathology.

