### **6.3 Surgery and Follow-up Visits**

#### ***Procedures at the time of surgery***

The following procedures will be performed on the day of surgery (before administration of anesthesia and before surgery):

- Record the patient's vital signs
- Obtain blood for routine laboratory tests
- Record all medications being taking, including prescription, over-the-counter, and herbal medications
- Discuss with the patient any new or unexpected changes they are feeling.
- Record any AEs.

Once the patient is under anesthesia, some procedures will occur that would not normally be part of surgery if the patient were not in this study. The SOC surgical procedures will be allowed to continue with the addition of the imaging steps listed below.

- If the primary tumor is not visually apparent using standard approaches, the NIR camera may be used to help locate and guide the resection of the primary tumor.
  - The primary tumor should be imaged prior to excision and following excision on a piece of normal tissue from a distance equal to the operating distance of the camera.
- If the primary tumor is apparent under standard conditions, it will be imaged prior to resection. Additionally, the resected tissue will be imaged using the

intraoperative camera on a section of normal tissue at a distance equal to the operating distance of the camera

- Following the primary tumor resection, margins (both on the excised primary and the affected lung) will be examined using NIR in an effort to detect residual disease
- All SOC lymph nodes to be collected during the operative procedure will be imaged prior to and following excision in a manner identical to the procedures used for imaging the primary resection
- Once the SOC primary tumor resection is complete, the surgeon will examine the thoracic cavity with the intraoperative NIR camera in search of additional fluorescent disease, or lymph nodes that were missed during SOC
- Additional fluorescent lesions, or lymph nodes will be imaged prior to excision, removed and imaged on a section of normal tissue in a manner analogous to the SOC specimens.
- For all resected specimens (including SOC primary tumor, margins, SOC lymph nodes and additional missed disease), fluorescence status and specimen name will be called out by the surgeon for documentation by the clinical research coordinator in the provided Imaging Workbook

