5. ANALYSIS ENDPOINTS

5.1 Efficacy Endpoints

5.1.1 Clinically Significant Event Endpoints

Performance metrics will include the identification of a CSE detected by pegasitacianine. CSEs will include pegasitacianine detection of primary tumors otherwise undetectable using SOC procedures, detection of occult disease not otherwise known by the surgeon to exist (as synchronous disease), the detection of a positive surgical margin, and accurate identification of tumor negative SOC biopsies. A list of CSEs and their definitions is provided below.

- **Detection of Synchronous Disease** – identification of tumor-containing tissue due to pegasitacianine fluorescence, confirmed via histopathological analysis, that otherwise went undetected during pre-operative imaging (PET, CT, MRI) or by the surgeon during SOC surgery.
 - This occurs when a specimen that comes from the thoracic cavity or lymph nodes, is (1) collected via fluorescence and (2) is pathologically-confirmed as a tumor. Note that any specimen collected from the thoracic cavity following SOC will be considered to be collected by fluorescence.

- Detection of Positive Surgical Margin – following the completion of SOC surgery, the surgical fields will be examined for residual fluorescence. Detection of a positive surgical margin would be those specimens collected as a result of residual pegsitacianine fluorescence following the completion of SOC surgery that return a histologically positive for tumor outcome.
 - This occurs when a margin specimen (either from the primary tumor or a lung resection margin) (1) is collected via fluorescence and (2) is pathologically-confirmed as a tumor. Note that any lung resection margin collected will be considered to be collected by fluorescence.
- Identification/Localization of the Primary Tumor – during SOC surgery, the surgeon will examine the affected lung to locate the primary tumor. If the primary tumor is not visually apparent using standard imaging methods the surgeon may use the NIR imaging device to aid in localization. If the NIR imaging identifies and/or locates the primary tumor, which was undetectable using SOC approaches, this will be deemed a CSE.
 - This occurs when the primary tumor is not located using SOC approaches, and is instead identified using NIR imaging.

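### Protocol 6.3 starts the near-infrared search for missed disease after the primary tumor resection alone, other sections wait for the lymph nodes or for all of SOC, and no rule says when a node counts as found by fluorescence

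*Protocol*

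**What the plan says.** Protocol 6.3 (Procedures at the time of surgery) gives this start for the search for missed disease: "Once the SOC primary tumor resection is complete, the surgeon will examine the thoracic cavity with the intraoperative NIR camera". The schedule in the Protocol Summary has nearly the same sentence with one more condition: "Once the SOC primary tumor and lymph node resection is complete, the surgeon will examine the thoracic cavity with the intraoperative NIR camera". The design text of the Protocol Summary is broader still: "Once SOC surgical resection is complete, the surgeon will use the NIR camera system to evaluate the thoracic cavity". Protocol 3.1 and SAP 3.1 repeat that broader condition.

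The camera is also in use before SOC ends. For the primary tumor, 6.3 says "If the primary tumor is apparent under standard conditions, it will be imaged prior to resection". The margins are examined once the primary is out. For nodes, 6.3 says "All SOC lymph nodes to be collected during the operative procedure will be imaged prior to and following excision".

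Synchronous disease is one of the four CSE types (Protocol 9.3, SAP 5.1.1). Its general definition asks for tumor that neither pre-operative imaging nor the surgeon during SOC had detected. Its operational line reads "This occurs when a specimen that comes from the thoracic cavity or lymph nodes, is (1) collected via fluorescence" and adds only confirmation by pathology. A note treats every thoracic cavity specimen taken after SOC as collected by fluorescence; it does not name nodes. One CSE of any type makes the subject a responder (SAP 5.1.1). The listing in SAP 7.10.2.1 shows whether a node was obtained by SOC or by fluorescence.

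**The concern.** There is no control arm. Each patient is his or her own control, and the SOC part of the operation is the control condition. The comparison works only if SOC is closed before findings are credited to the drug.

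If the cavity is scanned while planned SOC nodes are still in place, a tumor-bearing node that routine sampling would have removed can be taken as a fluorescent node and counted as synchronous disease. The label is assigned in an open-label setting, where the surgeon both selects the specimens and calls their fluorescence. Without a rule, error can run either way: an SOC node credited to the drug, or a drug-found lesion recorded as SOC. With up to five centers and no analysis by center (SAP 7.6), different readings of 6.3 would not show in the results. Protocol 9.1 says the trial is meant to inform power calculations for later studies, so an attribution error would carry forward.

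**Working it through.** **Step 1. The five statements of when the search starts.**
- Protocol 6.3: SOC primary resection complete.
- Protocol Summary, schedule: SOC primary and lymph node resection complete.
- Protocol Summary, design text: SOC surgical resection complete.
- Protocol 3.1: the same.
- SAP 3.1: the same.

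Section 6.3 is the least demanding of the five, and it is the visit-by-visit procedure.

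**Step 2. Follow one node through the rules.** A planned SOC node bears tumor and fluoresces. Under the synopsis order it is removed as SOC and gives no synchronous-disease CSE. Under a literal reading of 6.3 it may be seen in the cavity search first and removed for its fluorescence. The operational line asks two things: was it collected via fluorescence, and was it tumor? Both answers are yes. Nothing in that line asks whether SOC would have taken it. The automatic-credit note does not decide the case because it names cavity specimens, so the result rests on the SOC-or-fluorescence label, for which neither document gives a rule.

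**Step 3. Which results move.**
- Synchronous-disease rate, reported by type under SAP 7.10.1.1: moves directly.
- Any-CSE rate: moves only if the subject has no other CSE. A single non-fluorescent, tumor-negative SOC specimen already makes a responder.
- *Ex situ* sensitivity, specificity, PPV and NPV: unchanged for a node that would have been removed anyway, since it stays in the same cell of the two-by-two table whatever its label.

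**Step 4. Size.** The plan gives no figure to reproduce; n=40 has no alpha, power or effect size behind it. Taking all 40 subjects as evaluable:
- Shift per affected subject = 1/40 = 2.5 points in the synchronous-disease rate. With 30 evaluable it would be 1/30 = 3.3 points.
- For scale, with assumed counts and Clopper-Pearson intervals: 4/40 = 10.0% (95% CI 2.8 to 23.7); 5/40 = 12.5% (4.2 to 26.8).
- If a share r of affected subjects has another CSE, the expected shift in the any-CSE rate is 2.5 × (1 − r) points per affected subject. Assumed r of 0.25, 0.50 and 0.75 gives 1.9, 1.25 and 0.6 points.
- If each subject has chance q of such a misattribution, the expected number is 40q and the chance of at least one is 1 − (1 − q)^40.

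| q (assumed) | Expected subjects | Chance of at least one |
|---|---|---|
| 1% | 0.4 | 33.1% |
| 2.5% | 1 | 63.7% |
| 5% | 2 | 87.1% |
| 10% | 4 | 98.5% |

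The documents give neither q nor r, so these are ranges and not estimates.

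**The case against.** The best defense is that 6.3 does not order an early scan. Its steps list SOC node imaging before the cavity search, and the search is for nodes that SOC missed; a node still awaiting planned sampling has not been missed. The general CSE definition requires disease that otherwise went undetected. The SAP's Efficacy Population (SAP 6.3) requires the opportunity for evaluation of the cavity after SOC. Sponsor staff attend the first operations to keep procedures uniform. Imaging SOC tissue in place is a deliberate step, and the primary-localization CSE needs NIR during SOC.

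Much of this stands, and it rules out several stronger readings that a reader might infer:
- That sites searched early. The text permits this; it does not show that it happened.
- That the surgeon is still choosing SOC specimens while viewing the signal. The documents describe SOC nodules and nodes as already planned when they are imaged.
- That the SOC plan is not recorded anywhere. The Imaging Workbook is not available here. One can say only that the protocol and SAP do not require such a record.
- That the primary result is inflated by a known amount. Many affected subjects may be responders through another CSE, and no document gives the counts.

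The defense does not remove the conflict. The stated trigger in 6.3 names the primary alone, and nothing says that the listed steps must be followed in order. The safeguard in the general definition is absent from the operational line that a programmer would apply. The requirement for evaluation after SOC itself needs an identifiable end of SOC, which neither document requires to be recorded.

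**Conclusion.** The concern holds as an inconsistency between sections combined with a missing attribution rule. Its effect falls mainly on the synchronous-disease rate, at 2.5 points per affected subject if all 40 are evaluable. It reaches the any-CSE rate only through subjects with no other CSE. The total effect cannot be estimated from the documents, and its direction is upward only under the literal reading of 6.3; an unruled label can err both ways. The study tests no hypothesis, so no error rate is at stake. The point should be fixed because the boundary between SOC and the drug's contribution underlies part of the primary endpoint in an unblinded, single-arm trial. It does not undermine the trial as a whole.

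**What to change.** 1. Reconcile Protocol 6.3 with both parts of the Protocol Summary, Protocol 3.1 and SAP 3.1, so that one stated point ends the SOC phase before the credited cavity search starts.
2. In the existing Imaging Workbook, have the coordinator enter, at the surgeon's dictation, the planned SOC lesions and node stations before NIR is first used, and the time at which SOC is declared complete.
3. In Protocol 9.3 and SAP 5.1.1, set the node label and the synchronous-disease credit from that record. Tissue on the pre-NIR plan and taken before the recorded end of SOC is SOC. Tumor-positive tissue taken because of fluorescence after that time is credited to fluorescence. This includes a node left behind in a listed station once SOC sampling was declared complete; excluding every listed station outright would deny credit for disease that was truly missed.

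The cost is brief dictation by people already in the room, one workbook entry, and changes of wording. The CSE rate may come out slightly lower. SAP 3.1 notes that Part 2 was not opened, so the new record may help only remaining or future subjects; for those already operated on, the rule can use only what existing records show. SAP 7.1 allows updates before database lock and sends changes that may affect the primary conclusions to a protocol amendment, which is the right route for item 3.

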7.9.5 Surgery Details and Specimen Collection

Surgery details including the following will be summarized on a patient level using descriptive statistics in the Safety population:

- Duration of surgery
- Location of tumor

- Method of tumor localization, including number of subjects with primary tumor(s) identified using NIR imaging
- Number of SOC specimens collected
- Number of additional lung nodules/areas found as a result of NIR imaging following SOC procedures and confirmed to be cancer
- Number of SOC specimens collected, found to be negative for tumor, and did not fluoresce during *ex situ* imaging
- Number of areas with fluorescence removed on:
 - Lung resection margins
 - Thoracic cavity
 - Lymph nodes
 - Total (any area)
- Number of areas with fluorescence on lung resection margins
- Subjects with fluorescence observed anywhere in thoracic cavity
- Number of lymph nodes collected as SOC surgery
- Time spent imaging
- Camera system used

A listing will also be generated.

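### Protocol 6.3 lists removal of additional fluorescent lesions and nodes as a step, while 3.1 and the SAP leave it to the surgeon; if it stays optional, foci left in place drop out of PPV and specificity and are not tabulated.

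*Protocol*

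**What the plan says.** Two sets of passages govern the same moment in the operation, when the surgeon has finished SOC resection and finds further fluorescence.

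**Removal listed as a step.** Protocol 6.3 states: "Additional fluorescent lesions, or lymph nodes will be imaged prior to excision, removed and imaged on a section of normal tissue". The Schedule of Events in the Protocol Summary has a parallel line for lesions only: "Additional fluorescent lesions will be imaged prior to excision, removed, and then imaged on a section of normal tissue". Neither carries a discretion clause.

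**Removal optional.** Protocol 3.1 states: "If additional fluorescent foci are observed, the area may be resected at the discretion of the surgeon for pathological confirmation of disease". For nodes it adds: "Additional fluorescent lymph nodes, detected during the evaluation of the thoracic cavity, may also be collected and imaged". The Trial Design text of the Protocol Summary agrees: "the area may be resected, at the discretion of the surgeon, for pathological confirmation of disease". SAP 3.1 repeats that wording for foci and is equally permissive for nodes.

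Protocol 6.5, and the Training entry of the Protocol Summary, make the operating surgeon solely responsible for choosing specimens and calling their fluorescence.

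**Analysis.** Protocol 9.4 and SAP 5.1.2 compute sensitivity, specificity, PPV and NPV from collected specimens, SOC and guided together, against histology. SAP 7.4 uses observed cases with no imputation of missing data. SAP 7.9.5 has an item headed "Number of areas with fluorescence removed on", covering lung resection margins, thoracic cavity and lymph nodes. It also counts fluorescent areas present on lung margins, and subjects with any fluorescence in the cavity.

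**The concern.** Whether extra tissue is taken from a patient should not depend on which section a center reads. The Protocol Summary also disagrees with itself, since its Trial Design text and its Schedule of Events differ. Up to five centers may take part, and SAP 7.6 plans no analysis by center, so differing practice would not show in the results.

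The statistical issue arises under the optional reading. A false or true positive needs histology. A fluorescent focus left in the patient is therefore neither, and it leaves no trace in PPV or specificity. If the reasons for leaving a focus are related to whether it is tumor, the PPV of foci removed differs from the PPV of foci seen. Protocol 9.1 gives the study's purpose as informing power calculations for later studies, and Protocol 9.8 uses sensitivity and specificity in the interim review, so the difference could carry forward.

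**Working it through.** The documents give no figure to reproduce here. The sample size of 40 has no formula, and the study is not powered for a hypothesis test. The check is a comparison of text, followed by an illustration on assumed counts.

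**Step 1: the removal rule, side by side**

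| Place | Foci or lesions | Nodes |
|---|---|---|
| Protocol 6.3 | removed, no condition | removed, no condition |
| Protocol Summary, Schedule of Events | removed, no condition | not named in that line |
| Protocol Summary, Trial Design | optional | optional |
| Protocol 3.1 | optional | optional |
| SAP 3.1 | optional | optional |

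**Step 2: what SAP 7.9.5 would show**

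| Site | Fluorescent areas seen | Fluorescent areas removed |
|---|---|---|
| Lung resection margin | yes | yes |
| Thoracic cavity | subjects only | yes |
| Lymph nodes | no | yes |

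Seen can be set against removed for margins only. The workbook instruction in Protocol 6.3 covers resected specimens.

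**Step 3: bounds for unremoved foci.** All counts are assumptions: 20 additional glowing foci seen, 12 removed, 6 of those malignant, 8 left. For SOC specimens, assume 40 true positives, 10 false positives and 60 true negatives.

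Guided foci alone:
- PPV among removed = 6/12 = 50%
- the 8 left all benign: 6/20 = 30%
- the 8 left all tumor: (6 + 8)/20 = 14/20 = 70%

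Pooled, as the SAP plans it:
- PPV = (40 + 6)/(40 + 10 + 12) = 46/62 = 74%
- all benign: 46/(62 + 8) = 46/70 = 66%
- all tumor: (46 + 8)/70 = 54/70 = 77%

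The width is 40 points for guided foci and about 11 points pooled. With 16 of 20 removed and 8 malignant, guided PPV is 8/16 = 50% with bounds 8/20 = 40% and 12/20 = 60%. Pooled PPV is then 48/66 = 73% with bounds 48/70 = 69% and 52/70 = 74%.

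Specificity on the first set of counts is 60/(60 + 10 + 6) = 60/76 = 79%. If the 8 left were all benign it would be 60/84 = 71%; if all were tumor it would stay at 60/76.

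**Step 4: direction.** Let q be the tumor share of additional foci, and rt and rb the chances that a tumor focus and a benign focus are removed. All three are assumed. Then guided PPV = q·rt / (q·rt + (1 − q)·rb). Take q = 0.50, with 30 additional foci for the pooled column and the same SOC counts:

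| rt / rb | Guided PPV | Pooled PPV |
|---|---|---|
| 1.0 / 1.0 | 0.50 | 55/80 = 0.69 |
| 0.6 / 0.6 | 0.50 | 49/68 = 0.72 |
| 0.9 / 0.6 | 0.45/0.75 = 0.60 | 53.5/72.5 = 0.74 |
| 0.9 / 0.3 | 0.45/0.60 = 0.75 | 53.5/68 = 0.79 |
| 0.6 / 0.9 | 0.30/0.75 = 0.40 | 49/72.5 = 0.68 |

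PPV moves up or down with the removal pattern, and the documents say nothing about that pattern. Specificity behaves differently. With true negatives held fixed, dropping a benign glowing focus cannot lower TN/(TN + FP). Whether any such foci are dropped, and how many, is unknown.

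**The case against.** The best reply is that there is only one rule. Protocol 6.3 introduces its list as imaging steps, so the line may only give the order of imaging for foci already chosen for excision. The surgeon's sole responsibility for selecting specimens fits that reading. It is a plausible account of what was meant, but it does not settle the text. The Protocol Summary's version of the list has no such imaging lead-in, and removal is named as a step without condition. The same list in 6.3 uses permissive wording where a choice is meant, as for using the camera to find the primary tumor.

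A second reply is that the two halves of the point exclude each other: if every additional focus were removed, this selection would vanish. That is correct, and the statistical part is conditional on discretion. Discretion is, however, the wording the SAP carries.

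A third is that the plan says openly that it analyses collected specimens, in an unpowered pilot with no PPV success threshold. This stands as a reason to make the bounds a sensitivity analysis and leave the planned estimate as it is.

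A fourth is that the list in SAP 7.9.5 is not presented as exhaustive, a listing is promised, table shells are in a separate document, and the Imaging Workbook was not supplied. This also stands: the documents plan no tabulation of cavity or node foci left in place, but they do not show that counting them is impossible.

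**Conclusion.** The wording conflict is established from the text and needs to be reconciled. The loss of unremoved foci from PPV and specificity follows from the definitions if removal is discretionary. Its size cannot be derived. The percentages above rest on assumed counts and removal rates and show scale only.

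Four stronger readings are not supported:

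- *PPV is overstated.* A reader might infer that surgeons leave the foci they least believe. The documents give no reason for leaving a focus; site could be one, since Protocol 3.1 names contralateral lung and bronchi. The direction for PPV is open.
- *The reported PPV could be wrong by 20 points either way.* The 30% to 70% range belongs to guided foci alone, which the plan does not report separately. The planned PPV pools SOC specimens, and on the same assumptions its bounds are 66% to 77%.
- *The conflict extends to margins.* The Protocol Summary says "Resection of the suspicious or fluorescent margin is at the discretion of the surgeon", but the procedure lists only have margins examined and do not order their removal.
- *The primary endpoint shifts materially.* A synchronous-disease event does need a collected, confirmed specimen. But any SOC specimen that is dark and tumor-negative already makes the patient a responder, so the effect on the any-event rate is unsized and may be small.

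Sensitivity and specificity of 70% or more were also the condition for opening Part 2, but SAP 3.1 notes that Part 2 was not opened.

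**What to change.** 1. Reconcile Protocol 6.3, Protocol 3.1, both places in the Protocol Summary and SAP 3.1 so that one removal rule applies at all centers. The choice belongs to the sponsor and surgeons.
2. In the Imaging Workbook, record every fluorescent focus seen, with its site (margin, cavity or node) and whether it was removed.
3. In SAP 7.9.5, report foci seen, removed and not removed for each of the three sites.
4. In SAP 7.10.2.1, add a sensitivity analysis giving PPV, pooled and for guided foci, with bounds that count unremoved foci as all negative and then as all positive.
5. If enrollment is complete, do this from stored images and records where possible; otherwise state the limitation in the study report.

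The cost is a wording clarification, one workbook line per unremoved focus and a few table rows. The lower PPV bound will look less favorable than the planned estimate.
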